In addition, GLPG1690 demonstrated a strong time-dependent, irreversible inhibition potential against CYP2C8-mediated metabolism. This could likely lead to a pronounced interaction with a sensitive CYP2C8 probe substrate (increased exposure) if co-administered with a GLPG1690 dose of 600 mg q.d. in human.

No interaction by GLPG1690 is expected for renal uptake transporters organic cation transporter (OCT)2, organic anion transporter (OAT)1 and OAT3 and hepatic efflux transporters P-glycoprotein (P-gp) and breast cancer resistance protein (BCRP). For the hepatic uptake transporters organic anion transporter polypeptide (OATP) OATP1B1, OATP1B3, and OCT1, and efflux transporters MATE1 (hepatic/renal) and MATE2K (renal) a clinical interaction with GLPG1690 cannot be ruled out; however substantial interactions are not anticipated. For the intestinal efflux P-gp and BCRP transporters and the hepatic efflux bile salt export pump (BSEP) transporters an interaction cannot be ruled out.

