6.6.2. Clinical Laboratory Evaluations

Blood samples will be collected before IMP intake by venipuncture (or indwelling catheter) at the time points indicated in the Schedule of Activities provided in Section 6.11 (see also Section 6.1). In addition, urine samples for the clinical laboratory evaluations will be collected.

Subjects do not need to be fasted at the time of sampling, unless specifically indicated. Clinical laboratory evaluations will be performed by the central laboratory.

Blood and urine samples will be collected for the following clinical laboratory safety tests:

- Hematology: hematocrit, mean corpuscular volume (MCV), mean corpuscular hemoglobin (MCH), mean corpuscular hemoglobin concentration (MCHC), Hb, red blood cell count, white blood cell (WBC) count, WBC differential count (absolute and relative), and platelets.
- Coagulation: activated partial thromboplastin time and prothrombin time, INR.
- Clinical chemistry: random glucose, urea, creatinine, uric acid, sodium, potassium, calcium, chloride, phosphorus, AST, ALT, GGT, total bilirubin, alkaline phosphatase, lactate dehydrogenase, total serum bile acid, albumin, total proteins, triglycerides, cholesterol, high density lipoprotein, low density lipoprotein, amylase, lipase, low density lipoprotein, and creatine kinase (CK) (CK- muscle/brain [CK-MB] to be performed if CK is elevated).
- Urinalysis:
 - Dipstick: pH, glucose, proteins, blood, leucocytes;
 - Microscopic examination of the sediment (cylinders, erythrocytes, leucocytes), if indicated.
- Serology: hepatitis B surface antigen and hepatitis C antibody, and HIV 1 and HIV 2 antibodies only at screening. Positive hepatitis and HIV results should be reported by the investigator as required by local law. To assess eligibility, a positive hepatitis C antibody test should be confirmed by hepatitis C virus (HCV) RNA test.
- FSH test for females at screening to confirm menopause, if applicable.
- Urine pregnancy tests will be performed (only for WOCBP) on a monthly basis at home or at the clinical study center, with one additional test at the clinical study center at Visit 4. At screening, a serum pregnancy test (beta-human chorionic gonadotropin) will be performed. A positive urine pregnancy test needs to be confirmed as soon as possible by a serum pregnancy test (local sample; central sample to be sent as well).

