# 9.4.2.3. Handling Non-fasted Results

For laboratory tests like glucose, triglycerides and total serum bile acid that are sensitive to fasting, descriptive statistics and tabulations of Common Terminology Criteria for Adverse Events (CTCAE) toxicities (fasting only) will be shown by fasting status. Tabulations of scorings according to normal ranges will be created for both fasting and non-fasting results pooled. Laboratory results for which the fasting status is missing, will be considered as taken fasted

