# 9.4.2.4. Scoring According to Normal Ranges

All values will be compared to their matching normal ranges. The normal ranges provided by the central laboratory will be used and are available in the database. Values will be scored as abnormally low (L), normal (N) or abnormally high (H): the variable LBNRIND in SDTM.LB dataset will be used in the analysis.

For glucose, triglycerides and total serum bile acid in non-fasting state the following limits are to be used:

Tests	Thresholds
Glucose (non-fasting)	>= 200 mg/dL
Triglycerides (non-fasting)	>= 200 mg/dL
Total serum bile acid (non-fasting)	>x 3 ULN1

Only for tests for which no toxicity gradings are specified in Section 9.4.2.5, analysis of the classification according to normal ranges will be done. Except for fasting sensitive tests like glucose and triglycerides. These will be summarized with scorings based on CTCAE/other

<sup>1 ULN: upper limit of normal range, LLN: lower limit of normal range

gradings for the fasted samples only, but also with scorings according to normal ranges for fasting and non-fasting samples pooled.

Any clinical significance flags related to these values will only be listed.

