#### 9.4.2.5. Scoring Based on CTCAE/Other Gradings

CTCAE version 5.0 classification is only for the tests listed below.

Tests	Thresholds (Conventional Unit		Thresho (SI Unit	Thresholds (SI Units)		
Hematology						
Hemoglobin (anemia) decreased	<lln-10< td="">g/dL	<lln-100< td="">g/L	G1	</lln-100<>	</lln-10<>	g/dL	<lln-100< td="">g/L	G1	</lln-100<>	g/L	G1	
	<10 - 8 <8	g/dL g/dL	<100 -80 <80	g/L g/L	G2 G3	
Hemoglobin increased (increase above ULN)	Increase >0-2	g/dL	Increase >0-20	g/L	G1	
	Increase >2-4 Increase>4	g/dL g/dL	Increase >20-40 Increase>40	g/L g/L	G2 G3	
White blood cell (WBC) count decreased	<lln-3000< td="">/mm3	<lln-3.0< td="">* 10^9/L	G1	</lln-3.0<>	</lln-3000<>	/mm3	<lln-3.0< td="">* 10^9/L	G1	</lln-3.0<>	* 10^9/L	G1	
	<3000 - 2000 < 2000-1000 <1000	/mm3 /mm3 /mm3	<3.0-2.0 < 2.0-1.0 <1.0	* 10^9/L * 10^9/L * 10^9/L	G2 G3 G4	
White blood cell (WBC) count increased	>100,000	/mm3	>100.0	* 10^9/L	G3	
Neutrophils decreased	< LLN-1500	/mm3	< LLN-1.5	* 10^9/L * 10^0/I	G1 G2	
	< 1000-500	/mm3	< 1.0-0.5	* 10^9/L * 10^9/L * 10^0/L	G2 G3	
Lymphocytes decreased	< 500	/mm3	< 0.5	* 10^9/L * 10^9/L	G4 G1	
	< 800-500 < 500-200	/mm3 /mm3	< 0.8-0.5 < 0.5-0.2	* 10^9/L * 10^9/L	G2 G3	
	< 200	/mm3	< 0.2	* 10^9/L	G4	
Lymphocytes increased	> 4000 > 20,000	/mm3 /mm3	> 4.0 > 20.0	* 10^9/L * 10^9/L	G2 G3	
Eosinophils absolute count	>ULN		>ULN		G1	
Eosinophils relative count	> 7%		> 7%		G1	
Platelets decreased	< LLN-75000	/mm3	< LLN-75.0	* 10^9/L	G1	

CONFIDENTIAL

Doc id 402993

	< 75000 – 50000	/mm3	< 75.0 - 50.0	* 10^9/L	G2
	< 50000-25000	/mm3	< 50.0-25.0	* 10^9/L	G3
	< 25000	/mm3	< 25.0	* 10^9/L	G 4
Coagulation					
Activated partial	> ULN - 1.5 x UL	N	> ULN - 1.5 x U	LN	Gl
thromboplastin time	> 1.5 - 2.5 x ULN	[	> 1.5 - 2.5 x ULN		G2
(aPTT)	> 2.5  x ULN		> 2.5  x ULN		G3
	> ULN - 1.5 x UL	N	> ULN - 1.5 x U	LN	
Prothrombin time (PT)	> 1.5 - 2.5 x ULN		> 1.5 - 2.5 x ULM	V	/
	> 2.5 x ULN		> 2.5 x ULN		
	1.2 – 1.5 xULN		> 1.2 - 1.5 xULN	1	G1
INR increased	> 1.5 - 2.5 xULN		> 1.5 - 2.5 xULN	ſ	G2
	> 2.5 xULN		> 2.5  xULN		G3
Chemistry					
Glucose decreased	< LLN – 55	mg/dL	< LLN - 3.0	mmol/L	G1
	< 55 - 40	mg/dL	< 3.0-2.2	mmol/L	G2
	< 40 - 30	mg/dL	< 2.2 -1.7	mmol/L	G3
	< 30	mg/dL	< 1.7	mmol/L	G4
Glucose increased (fasting)	> 130	mg/dL	> 7.2	mmol/L	/
	> ULN - 1.5 x UL	Ŋ	> ULN - 1.5 x U	G1	
Constitution in success 1	>1.5-3x ULN		>1.5-3x ULN		G2

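### SAP 9.4.2.3 and 9.4.2.4 grade glucose on fasted samples only, so low glucose in samples recorded as non-fasted gets no CTCAE grade, and other SAP sections conflict with that rule

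*SAP*

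**What the plan says.** **Sampling.** Protocol 6.6.2 lists "Clinical chemistry: random glucose, urea, creatinine, uric acid" among the central-laboratory tests and states: "Subjects do not need to be fasted at the time of sampling, unless specifically indicated".

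**Grading rule.** SAP 9.4.2.3 names glucose, triglycerides and total serum bile acid as sensitive to fasting and says that "tabulations of Common Terminology Criteria for Adverse Events (CTCAE) toxicities (fasting only) will be shown by fasting status". It treats a missing fasting status as fasted. SAP 9.4.2.4 repeats the restriction for glucose and triglycerides: CTCAE or other "gradings for the fasted samples only, but also with scorings according to normal ranges for fasting and non-fasting samples pooled".

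**Normal-range rule.** SAP 9.4.2.4 first scores every value low, normal or high against the central-laboratory range. It then gives separate limits for the non-fasting state. For glucose there is one, at or above 200 mg/dL, with no lower limit.

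**Grade table.** In SAP 9.4.2.5 the row for decreased glucose runs from G1 to G4, with cut-points at the lower limit of normal (LLN), 55, 40 and 30 mg/dL, and has no fasting label. The row that begins "Glucose increased (fasting" is labelled fasting and has a single threshold of 130 mg/dL with no grade. The triglyceride row is also labelled fasting.

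**Derivation and tables.** SAP 9.4.2.7.2 takes the worst grade over all non-missing post-baseline records except local-laboratory results. SAP 9.4.2.8 limits the normal-range shift and frequency tables to tests that have no CTCAE grades, and provides the CTCAE tables for selected tests that it does not name.

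**The concern.** Restricting grades to fasted samples makes sense for high glucose and triglycerides, because a recent meal raises both and a random high value is hard to interpret. It does not make sense for low glucose: eating is no reason to discount a low reading. Since the high-glucose row has no numbered grade, the rule removes G1-G4 grades only in the direction where fasting status gives no ground for doing so.

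What is at stake is the by-arm count of graded low glucose. With no fasting required, some routine samples will be recorded as non-fasted, and low values in them drop out of that count. The sections also disagree. A programmer following 9.4.2.3 and 9.4.2.4 and one following 9.4.2.5 and 9.4.2.7.2 could produce different counts from the same data.

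**Working it through.** **Grade limits.** Dividing by 18.016, 55, 40 and 30 mg/dL become 3.05, 2.22 and 1.67 mmol/L. The SAP prints 3.0, 2.2 and 1.7, so the row agrees with itself after rounding.

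**One value traced through the rules.** Take a central-laboratory glucose of 38 mg/dL, which lies in the G3 band (below 40, down to 30).

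| Recorded status | 9.4.2.3 and 9.4.2.4 | 9.4.2.5 row with 9.4.2.7.2 |
|---|---|---|
| Fasted | G3 | G3 |
| Missing | G3 (counts as fasted) | G3 |
| Non-fasted | no grade | G3 |

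The sections differ only in the last line.

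**Does the non-fasted value appear as L?** Two readings are open.

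- *Yes.* 9.4.2.4 scores all values against the laboratory range and promises a tabulation with fasted and non-fasted samples pooled. 9.4.2.7.1 counts a subject as L after any one low result.
- *Not assured.* 9.4.2.4 then prescribes the non-fasting limits without saying whether they replace the laboratory range or add to it, and for glucose they contain no lower bound. Read literally, 9.4.2.8 also drops glucose from the normal-range tables, because glucose has grades.

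On the first reading, 38 mg/dL and a value just under the LLN both show as L.

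**Share of low results left ungraded.** The documents do not give the inputs, so both are assumptions:

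- q = share of glucose samples recorded as non-fasted;
- r = rate of low glucose in non-fasted samples divided by the rate in samples that are fasted or of missing status.

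Share ungraded = q·r / (q·r + 1 − q).

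| r | q = 0.1 | q = 0.5 | q = 0.9 | q above which the share exceeds 50% = 1/(1 + r) |
|---|---|---|---|---|
| 1 | 10% | 50% | 90% | 0.50 |
| 0.5 | 5% | 33% | 82% | 0.67 |
| 0.25 | 3% | 20% | 69% | 0.80 |

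Example: q = 0.5 and r = 0.5 give 0.25 / (0.25 + 0.5) = 33%. With r = 1 the share is simply q. These are shares of results, not subjects; a subject with another low value in a fasted sample would still be counted.

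**The case against.** Four arguments weigh against the point.

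1. **The value is still scored.** 9.4.2.4 compares all values with the laboratory range, expressly excepts glucose from the rule that drops normal-range analysis for graded tests, and promises a pooled tabulation. That specific exception arguably governs the general wording of 9.4.2.8. This stands to the extent that it would be wrong to say non-fasted glucose has only an upper limit. It does not restore the grade, and the SAP should not leave the L to inference.
2. **Adverse-event reporting is a second route.** Protocol 6.6.2 and 9.1.5 require clinically significant abnormalities to be recorded as adverse events, and these are graded and tabulated by arm. This limits the harm. But the route depends on the investigator's judgement, and Protocol 9.2.2 grades such events on clinical severity, which need not match the laboratory grade.
3. **A graded glucose table may not exist,** since 9.4.2.8 covers only selected, unnamed tests. However, 9.4.2.4 says glucose is summarised with grades.
4. **The consequence is small.** The studies were halted, the report is abbreviated, and laboratory data carry no inferential tests. This stands and sets the severity. Safety endpoints are nevertheless retained (SAP section 1).

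Two stronger readings are tempting. A reader might infer that most low-glucose results are lost because sampling is random. The documents do not show this: they give no non-fasted share, and missing status is graded as fasted. A reader might also infer a specific hypoglycaemia risk, since Protocol 2.1.3 says "GLPG1690 demonstrated a strong time-dependent, irreversible inhibition potential against CYP2C8-mediated metabolism" and Appendix 3 names repaglinide, rosiglitazone and pioglitazone as substrates. Appendix 3 lists those drugs as excluded and prohibited, and exclusion criterion 9 bars subjects taking such substrates. That argument does not support the point, which does not need it.

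**Conclusion.** The point holds in limited form and is minor. As written, SAP 9.4.2.3 and 9.4.2.4 withhold a G1-G4 grade from low glucose in any sample recorded as non-fasted. This conflicts with the unlabelled row in 9.4.2.5 and with the worst-grade derivation in 9.4.2.7.2. Whether such a value is even tabulated as L is unclear.

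The size cannot be fixed from the documents. Over the assumed ranges q = 0.1 to 0.9 and r = 0.25 to 1, the share of low results left ungraded runs from 3% to 90%. It equals the non-fasted share when low values are equally frequent in both states, and falls below it when they are rarer after food. The calculation assumes that r does not exceed 1.

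Only the laboratory safety tables are affected. The primary and key secondary analyses, the alpha split and the sample size are untouched.

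**What to change.** Make four edits to the SAP:

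- In 9.4.2.3 and 9.4.2.4, limit the fasted-only grading rule to increased glucose and triglycerides. Total serum bile acid has no row in 9.4.2.5, so it needs no change here.
- In 9.4.2.5, state that decreased glucose is graded on all central-laboratory samples whatever the fasting status. This also agrees with 9.4.2.7.2.
- In 9.4.2.4, state that the laboratory LLN still applies to non-fasted glucose and that the 200 mg/dL limit replaces only the upper bound.
- In 9.4.2.8, except glucose and triglycerides from the restriction to ungraded tests, so that the pooled normal-range tabulation is actually produced, and name glucose among the tests selected for the CTCAE tables.

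The cost is a few sentences and a small programming change. No new data are needed.

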#### 9.4.2.5. Scoring Based on CTCAE/Other Gradings

CTCAE version 5.0 classification is only for the tests listed below.

Tests	Thresholds (Conventional Unit		Thresho (SI Unit	Thresholds (SI Units)		
Hematology						
Hemoglobin (anemia) decreased	<lln-10< td="">g/dL	<lln-100< td="">g/L	G1	</lln-100<>	</lln-10<>	g/dL	<lln-100< td="">g/L	G1	</lln-100<>	g/L	G1	
	<10 - 8 <8	g/dL g/dL	<100 -80 <80	g/L g/L	G2 G3	
Hemoglobin increased (increase above ULN)	Increase >0-2	g/dL	Increase >0-20	g/L	G1	
	Increase >2-4 Increase>4	g/dL g/dL	Increase >20-40 Increase>40	g/L g/L	G2 G3	
White blood cell (WBC) count decreased	<lln-3000< td="">/mm3	<lln-3.0< td="">* 10^9/L	G1	</lln-3.0<>	</lln-3000<>	/mm3	<lln-3.0< td="">* 10^9/L	G1	</lln-3.0<>	* 10^9/L	G1	
	<3000 - 2000 < 2000-1000 <1000	/mm3 /mm3 /mm3	<3.0-2.0 < 2.0-1.0 <1.0	* 10^9/L * 10^9/L * 10^9/L	G2 G3 G4	
White blood cell (WBC) count increased	>100,000	/mm3	>100.0	* 10^9/L	G3	
Neutrophils decreased	< LLN-1500	/mm3	< LLN-1.5	* 10^9/L * 10^0/I	G1 G2	
	< 1000-500	/mm3	< 1.0-0.5	* 10^9/L * 10^9/L * 10^0/L	G2 G3	
Lymphocytes decreased	< 500	/mm3	< 0.5	* 10^9/L * 10^9/L	G4 G1	
	< 800-500 < 500-200	/mm3 /mm3	< 0.8-0.5 < 0.5-0.2	* 10^9/L * 10^9/L	G2 G3	
	< 200	/mm3	< 0.2	* 10^9/L	G4	
Lymphocytes increased	> 4000 > 20,000	/mm3 /mm3	> 4.0 > 20.0	* 10^9/L * 10^9/L	G2 G3	
Eosinophils absolute count	>ULN		>ULN		G1	
Eosinophils relative count	> 7%		> 7%		G1	
Platelets decreased	< LLN-75000	/mm3	< LLN-75.0	* 10^9/L	G1	

CONFIDENTIAL

Doc id 402993

	< 75000 – 50000	/mm3	< 75.0 - 50.0	* 10^9/L	G2
	< 50000-25000	/mm3	< 50.0-25.0	* 10^9/L	G3
	< 25000	/mm3	< 25.0	* 10^9/L	G 4
Coagulation					
Activated partial	> ULN - 1.5 x UL	N	> ULN - 1.5 x U	LN	Gl
thromboplastin time	> 1.5 - 2.5 x ULN	[	> 1.5 - 2.5 x ULN		G2
(aPTT)	> 2.5  x ULN		> 2.5  x ULN		G3
	> ULN - 1.5 x UL	N	> ULN - 1.5 x U	LN	
Prothrombin time (PT)	> 1.5 - 2.5 x ULN		> 1.5 - 2.5 x ULM	V	/
	> 2.5 x ULN		> 2.5 x ULN		
	1.2 – 1.5 xULN		> 1.2 - 1.5 xULN	1	G1
INR increased	> 1.5 - 2.5 xULN		> 1.5 - 2.5 xULN	ſ	G2
	> 2.5 xULN		> 2.5  xULN		G3
Chemistry					
Glucose decreased	< LLN – 55	mg/dL	< LLN - 3.0	mmol/L	G1
	< 55 - 40	mg/dL	< 3.0-2.2	mmol/L	G2
	< 40 - 30	mg/dL	< 2.2 -1.7	mmol/L	G3
	< 30	mg/dL	< 1.7	mmol/L	G4
Glucose increased (fasting)	> 130	mg/dL	> 7.2	mmol/L	/
	> ULN - 1.5 x UL	Ŋ	> ULN - 1.5 x U	G1	
Constitution in success 1	>1.5-3x ULN		>1.5-3x ULN		G2
Creatinine increased	> 3 - 6x ULN		> 3 - 6x ULN	> 3 – 6x ULN	
	> 6x ULN		$> 6 \mathrm{x} \mathrm{ULN}$		G 4
eGFR / Creatinine Clearance	< LLN-60	ml/min	< LLN-60	ml/min	G1
ml/min/1.73 m2	<60-30	ml/min	<60-30	ml/min	G2
	< 30 - 15	ml/min	< 30 -15	ml/min	G3
	< 15	ml/min	< 15	ml/min	G 4
Sodium decreased	<lln -="" 130<="" td="">mmol/L	<lln -="" 130<="" td="">mmol/L	G1	</lln>	</lln>	mmol/L	<lln -="" 130<="" td="">mmol/L	G1	</lln>	mmol/L	G1
	< 130 - 125	mmol/L	< 130 - 125	mmol/L	G2
	< 125 - 120	mmol/L	< 125 - 120	mmol/L	G3
	< 120	mmol/L	< 120	mmol/L	G4
Sodium increased	> ULN - 150	mmol/L	> ULN - 150	mmol/L	Gl
Southin moreused	> 150 - 155	mmol/L	> 150 - 155	mmol/L	G2
	> 155 - 160	mmol/L	> 155 - 160	mmol/L	G3

Galapagos GLPG1690-CL-303 & 304 CONFIDENTIAL

	> 160	mmol/L	> 160	mmol/L	G4
Potassium decreased	< LLN - 3	mmol/L	< LLN - 3	mmol/L	G1
	< 3 - 2.5	mmol/L	< 3 - 2.5	mmol/L	G3
	< 2.5	mmol/L	< 2.5	mmol/L	G4
Potassium increased	> ULN - 5.5	mmol/L	> ULN - 5.5	mmol/L	G1
	> 5.5 - 6	mmol/L	> 5.5 - 6	mmol/L	G2
	> 6 - 7	mmol/L	> 6 - 7	mmol/L	G3
	> 7	mmol/L	> 7	mmol/L	G4
Calcium decreased	< LLN - 8	mg/dl	< LLN - 2.0	mmol/L	G1
	< 8-7	mg/dl	< 2-1.75	mmol/L	G2
	< 7-6	mg/dl	< 1.75-1.5	mmol/L	G3
	< 6	mg/dl	< 1.5	mmol/L	G4
Calcium increased	> ULN - 11.5	mg/dl	> ULN - 2.9	mmol/L	G1
	> 11.5 - 12.5	mg/dl	> 2.9 - 3.1	mmol/L	G2
	> 12.5 - 13.5	mg/dl	> 3.1 - 3.4	mmol/L	G3
	> 13.5	mg/dl	> 3.4	mmol/L	G4
AST	>ULN-3 x ULN		>ULN-3 x ULN		G1
	> 3 - 5 xULN		> 3 - 5 xULN		G2
	> 5 -20 xULN		> 5 - 20 xULN		G3
	> 20  xULN		> 20  xULN		G4
ALT	>ULN-3 x ULN		>ULN-3 x ULN		G1
	> 3 -5 xULN		> 3 -5 xULN;		G2
	> 5 - 20 xULN		> 5 - 20 xULN		G3
	> 20  xULN		> 20  xULN		G4
GGT	$>$ ULN $- 2.5 \times UL$	.N	> ULN $- 2.5  x U$	LN	G1
	>2.5 -5 x ULN		>2.5 -5 x ULN		G2
	> 5 - 20 *ULN		> 5 - 20 *ULN		G3
	> 20 *ULN		> 20 *ULN		G4
Total bilirubin	$>$ ULN $- 1.5 \times UL$	.N	> ULN – 1.5 x U	LN	G1
	> 1.5 -3 x ULN		> 1.5 -3 x ULN		G2
	> 3-10 x ULN		> 3-10 x ULN		G3
	> 10 x ULN		>10 x ULN		G4
Alkaline phosphatase	$>$ ULN $- 2.5 \times UL$	N	$>$ ULN $- 2.5 \times U_{2}$	LN	G1
(aP)	>2.5 - 5 x ULN		>2.5 - 5 x ULN		G2
	>5 -20 x ULN		>5 -20 x ULN		G3
	> 20 x ULN		>20 x ULN		G4
Albumin	< LLN - 3	g/dL	< LLN - 30	g/L	G1
	< 3 - 2	g/dL	< 30 - 20	g/L	G2
	< 2	g/dL	< 20	g/L	G3

Triglycerides	>150 - 300	mg/dL	> 1.71 - 3.42	mmol/L	G1
(fasting)	> 300 - 500	mg/dL	> 3.42 - 5.7	mmol/L	G2
	> 500 - 1000	mg/dL	> 5.7 - 11.4	mmol/L	G3
	> 1000	mg/dL	> 11.4	mmol/L	G 4
Cholesterol	> ULN - 300	mg/dL	> ULN - 7.75	mmol/L	Gl
	> 300 - 400	mg/dL	> 7.75 - 10.34	mmol/L	G2
	> 400 - 500	mg/dL	> 10.34 - 12.92	mmol/L	G3
	> 500	mg/dL	> 12.92	mmol/L	G4
High density lipoprotein (HDL)	< 60	mg/dL	< 1.554	mmol/L	
Low density lipoprotein (LDL)	> 160	mg/dL	> 4.144	mmol/L	
	> ULN - 2.5 x U	LN	> ULN - 2.5 x UI	LN	Gl
Creating tripses (CV)	>2.5 -5 x ULN		>2.5 -5 x ULN		G2
Creatine kinase (CK)	> 5 - 10  x ULN		> 5 - 10  x ULN		G3
	$> 10 \mathrm{~x~ULN}$		> 10  x ULN		G 4

LLN=lower limit of normal range, ULN=upper limit of normal range

The following criteria will be used for Ccr.

Tests	Thresholds	Grade	Terms
C Cr (in mL/min)	≥90	G1	Normal or high
	60 to <90	G2	Mildly decreased
	45 to <60	G3a	Mildly to moderately decreased
	30 to <45	G3b	Moderately to severely decreased
	15 to <30	G4	Severely decreased
	<15	G5	Kidney failure

#### 9.4.2.6. Handling of Urinalysis Results

Results of urinalysis with qualitative results will be tabulated by time point. No toxicity grading or non-graded abnormalities will be derived.

#### 9.4.2.7. Worst-Case Abnormality

#### 9.4.2.7.1. According to Normal Range

The worst-case postbaseline will be determined per subject, per laboratory test (and sense, if below and above) and for each analysis period. All non-missing postbaseline values (including unscheduled and follow-up visits, but excluding local laboratory results) will be used to derive the following worst-case:

- L = low: at least one post-baseline result is classified as L.
- N = normal: all post-baseline results are classified as N.

- H = high: at least one post-baseline result is classified as H.

If, for a subject, both L and H are reported, the subject will be counted twice in the table: once with a worst-case L and once with a worst-case H.

Tables will be created for treatment-emergent abnormalities, i.e. postbaseline abnormalities which differ from (and are not better than) the baseline result. If the baseline result is missing, a postbaseline abnormality L or H will always be considered as treatment-emergent.

# 9.4.2.7.2. According to CTCAE Toxicity Grades

The worst-case postbaseline toxicity grade 0, 1, 2, 3 or 4 will be determined per subject, per laboratory test (and sense, if below and above) and for each analysis period, using all non-missing postbaseline records (including unscheduled and follow-up visits, but excluding local laboratory results).

The worst-case toxicity grade is the highest toxicity grade scored for the laboratory test (in each sense, if below and above).

Tables will be created for treatment-emergent toxicity grades. A postbaseline toxicity grade 1, 2, 3 or 4 is defined as treatment-emergent when higher than the toxicity grade of the baseline result. If the baseline result is missing, a postbaseline toxicity grade 1, 2, 3 or 4 will always be considered as treatment-emergent.

# 9.4.2.8. Analyses

No formal inferential statistics (p-values) will be derived.

For each laboratory test, descriptive statistics and graphical presentation (line plot of the mean and SE) will be provided for the actual laboratory values and change from baseline over time-by-treatment group.

A summary table per laboratory test category (hematology, biochemistry, urinalysis and coagulation), laboratory test and unit, treatment group and time point, showing only the mean value of actual values and changes from baseline will also be provided.

All laboratory abnormalities after the first dose of IP up to 30 days after the last dose will be included, consistently with AE reporting.

A shift table per laboratory test category (hematology, biochemistry, urinalysis and coagulation), laboratory test and treatment group will be provided for laboratory tests with normal ranges, for which CTCAE grades are not available. The table will present the worst shift in abnormality (L/N/...) during the treatment period versus the baseline abnormality (L/N/H).

Frequency table will be provided of the worst treatment-emergent laboratory abnormalities per laboratory test category (hematology, biochemistry, urinalysis and coagulation), laboratory test, and treatment group. This table will be created for those laboratory tests for which CTCAE grades are not available.

A shift table per laboratory test category (hematology, biochemistry and coagulation), laboratory test and treatment group for CTCAE grades will also be provided for selected tests only. The table will present the worst shift in CTCAE toxicity grade during the treatment period versus the baseline value.

A frequency table of the worst treatment-emergent laboratory CTCAE toxicity grades per laboratory test category (hematology, biochemistry and coagulation), laboratory test, and treatment group will be provided for selected tests only.

Shift table per laboratory test category (hematology, biochemistry, and urinalysis), laboratory test, and treatment group for laboratory tests with categorical data. The table will present the worst shift in value during the treatment period versus the baseline value.

